7.0 Treatment Protocol

7.1. Study Outline

We will screen and consent eligible patients of treating physicians at WCI and WCI-affiliated centers.

For Aim 1, the study team will conduct an in-person or zoom/phone interview for 30-60 minutes. First, we will explain the rationale of the study. Second, we will conduct an interview to elicit preferences and information regarding the ACP intervention.

For Aim 2, the study subject and caregiver (if applicable) will complete demographics and baseline measures. Following this, a telehealth visit will be scheduled with their oncology provider within 1-2 months of enrollment. If the patient does not have access to an electronic device, the study team will provide them with a tablet that is preloaded with the zoom application and internet access (if needed). Instructions on how to use zoom on the tablet will be provided. The sole purpose of the tablet is to allow for a zoom visit to occur and no data will be obtained and stored. If the tablet is lost or broken, we will provide a replacement tablet (and the broken tablet will be collected). We will work with the University IT to restrict the use of the tablets to zoom only.

During the ACP visit, their oncology provider will discuss ACP and EOL care. This visit will be recorded. Prior to the visit, providers will be provided with a checklist of items to discuss and summary of aging-related vulnerabilities. After the visit, the study subject and caregiver (if applicable) will complete post-intervention measures. They will be asked to mail back the tablet or return the tablet in the next in-person visit.

Within 4 weeks (up to 12 weeks if needed) of the telehealth visit, we will conduct an interview with the patient and caregiver (if applicable) either in-person or via zoom/phone for 30-60 minutes. We will also conduct an interview with the oncology provider who enrolled the patient on the study. All parties present for the recorded visit, including: enrolled patients, any accompanying caregivers, family or friends, the oncologist, and any other physicians or health care providers not participating in the study will be fully aware that the conversation is being audio-recorded before any recording begins, in addition to the prior written consent of enrolled patients. Patients, caregivers, and oncology providers may receive copies of these recordings at their request. Participants will complete post-intervention measures within 4 weeks of the visit (up to 12 weeks if needed).

7.2. Assessments of the Participants

Demographic, clinical, and cancer characteristics will be collected on paper or via RedCap.

7.2.1. Demographics (Patient, Caregivers, and Providers)

Patient and caregiver's age, race, ethnicity, gender, highest level of education achieved, employment status, and marital status. Caregiver's relationship to the patient will also be inquired. This will only be collected at baseline.

Provider's age, race, ethnicity gender, years in practice since completion of training, and disciplines (e.g., oncology physician, palliative care physician, APP, nurse) will be collected.

7.2.2. Clinical and Cancer Characteristics (Patient)

ECOG performance status, comorbidity, medications, weight, height, BMI, diagnosis and date of diagnosis, prior hematologic malignancies, cytogenetic risk group, and treatment regimen will be abstracted from the medical records. This information will only be collected at baseline.

In addition, we will collect the following from the medical records. We have previously collected this information in a retrospective fashion and will use similar procedures to extract this information prospectively from the medical records.

- Rate of hospice enrollment (and timing relative to death)
- Rate of palliative care referral (and timing relative to diagnosis)
- Rate of chemotherapy administration within the last 2 weeks of life
- Completion of advance directives which include MOLST forms, living will, durable power of attorney for healthcare, and healthcare proxy forms.
Documentation of ACP conversation in the electronic medical record will also be collected.
- Do no resuscitation order (and timing related to diagnosis and death)
- Percentage of patients who died from cancer with more than one emergency department visit in the last 30 days of life
- Percentage of patients who died from cancer admitted to the ICU in the last 30 days of life
- Hospitalization in the last 30 days of life (number of hospitalizations, reasons for hospitalizations)
- Use of life-sustaining treatments (e.g., mechanical ventilation, vasopressors, tracheostomy, dialysis for acute kidney injury, percutaneous endoscopic gastrostomy) in the last 30 days of life
- Transfusion in the last 7 days of life
- Place of death (home, hospital, facility, etc.)
- Inpatient mortality rate

7.2.3. Measures

Measures will be collected via in-person, or mailed to the participants.

7.2.3.1. Functional Status (Patient) – baseline only

Activities of daily living (ADL): ADLs are measures of self-care. ADL independence will be assessed using the Katz Index of Independence in Activities of Daily Living, commonly referred to as the Katz ADL. The Katz ADL is the most appropriate instrument to assess functional status as a measurement of the client's ability to perform activities of daily living independently. Clinicians

typically use the tool to detect problems in performing activities of daily living and to plan care accordingly. The Index ranks adequacy of performance in the six functions of *bathing, dressing, toileting, transferring, continence, and feeding*. Clients are scored yes/no for independence in each of the six functions. A score of 6 indicates full function, 4 indicates moderate impairment, and 2 or less indicates severe functional impairment.²⁵

Instrumental Activities of Daily Living (IADL): Self-reported functional status will be assessed using the IADL subscale of the Multidimensional Functional Assessment Questionnaire: Older American Resources and Services (OARS). The IADL subscale consists of seven questions rated on a three-point Likert scale. It measures the degree to which an activity can be performed independently.²⁶

Fall History: A self-reported history of falls in the past year will be recorded. A history of a recent fall has been demonstrated to be independently predictive of increased risk for chemotherapy toxicity in older cancer patients.²⁷

7.2.3.2. Psychological Health (Patient and Caregiver) – baseline and post-intervention

General Anxiety Disorder-7: A 7-item screening tool for anxiety.²⁸

Patient Health Questionnaire-9 (PHQ-2): A 9-item valid and reliable screening tool depression in the general population.²⁹

Distress: A self-reported tool to screen for symptoms of distress, using a 0-10 rating scale.³⁰

7.2.3.3. Social Support (Patient) – baseline only

OARS Medical Social Support: A 13-item questionnaire for patients regarding persons involved in medical social support as well as perception of overall support.^{31,32}

Patients also self-report their living situation and their main social support.

7.2.3.4. Nutritional status (Patient) – baseline only

Self-reported weight loss in the past 6 months

7.2.3.5. Cognition (Patient) – baseline only

BLESSED (baseline only): A screening tool for cognitive impairment in older adults.³³

7.2.3.6. Satisfaction with Communication (Patient and caregiver) – post-intervention only

Health Care Climate Questionnaire (HCCQ): A questionnaire assessing patients' and caregivers' satisfaction with patient-oncologist communication.^{34,35}

Heard and understood question: A self-report measure for seriously ill patients and their caregivers to report how well they feel heard and understand.³⁶

7.2.3.7. Therapeutic alliance (Patient) – post-intervention only

Modified Human Connection Scale: A survey to measure the extent to which patients and caregivers feel a sense of mutual understanding, caring, and trust with their physicians.³⁷

7.2.3.8. Goal-Concordant care (Patient) – post-intervention only

SUPPORT Survey: The Study to Understand Prognoses and Preferences for Outcomes and Risk of Treatments (SUPPORT) survey to assess if patient values align with current medical care.³⁸

7.2.3.9. Usability (Patient and caregiver) – post-intervention only

Telehealth Usability Questionnaire: A questionnaire assessing the usability of telehealth implementation.³⁹

7.2.3.10 Peaceful Acceptance of Illness (Patient) – post-intervention only

PEACE Questionnaire: Peace, Equanimity, and Acceptance in the Cancer Experience (PEACE) questionnaire to measure the extent to which patients with advanced cancer have a sense of peaceful acceptance of their terminal illness.⁴⁰

7.2.3.11. Acceptability (Patient and clinician) – post-intervention only

Patient Acceptability Questionnaire: A questionnaire used to assess the impact of the serious illness conversation on the patient's understanding and perception of their diagnosis.⁴¹

Clinician Acceptability Questionnaire: A questionnaire used implementation to assess the clinicians experience in using the SICP with patients.⁴¹

7.2.3.12 Confidence (Provider) – baseline and post-intervention

Clinician Confidence Questionnaire: A questionnaire used to assess clinician's self-perceived ability to implement the SICP in real practice.⁴¹

7.2.3.13. Health Literacy (Patient and caregiver) – baseline only

Cancer health literacy (CHLT-6): A brief instrument to determine whether an individual has limited cancer health literacy.⁴²

7.2.3.14 Quality of Life (Patient and caregiver) – baseline and post-intervention

Functional Assessment of Cancer Therapy-Leukemia (FACT-Leu): The FACT-Leu scale was created by combining the Functional Assessment of Cancer Therapy-General module (FACT-G) and a sub-scale made up of 17 leukemia-specific items.⁴³ It been tested and determined to be a valid, reliable, and efficient

instrument for evaluating leukemia-specific health-related QoL. This will be used for patients.

Caregiver Quality of Life Index-Cancer: The instrument self-reported health-related QoL.⁴⁴ This will be used for caregivers.

7.2.2.15. Disease Understanding (Patient, caregiver, and clinician) – baseline and post intervention

Disease Understanding – Patient (baseline and post-intervention): A questionnaire assessing patient's prognostic understanding of illness. They will also be asked if prognostic information was provided.

Disease Understanding – Caregiver (baseline and post-intervention): A questionnaire assessing caregiver's prognostic understanding of illness. They will also be asked if prognostic information was provided.

Disease Understanding – Provider (post-intervention only): A physician-facing questionnaire assessing patient prognosis. They will also be asked if prognostic information was provided.

7.2.2.16. ACP Engagement Survey (Patient) – baseline and post-intervention – Aim 2

ACP Engagement Survey: 15-item engagement survey that assess patient self-efficacy and readiness for identification of a medical decision maker, identification of personal values, and flexibility in decision making and communication with their physician.

7.2.2.17. Feasibility metrics

Feasibility metrics will be collected:

- Retention rate (percentage of patients consented to the study ultimately completing all study components) – primary metric
- Recruitment rate (percentage of patients who are approached and agree to enroll) will also be described

8.0 Data Handling and Statistical Considerations

8.1. Data Handling

8.1.1. The same protocols and procedures for data quality and control that are readily used for the NCI Community Oncology Research Program (NCORP) Research Base protocols currently being overseen by our office (which have accrued over 1,000 patients in the previous year) will be used for this study. Patients will fill out forms generated from RedCap and this information will be entered into RedCap (Section 9.5). Study personnel will perform BLESSED and the scores will be entered into RedCap.

8.1.2. It is anticipated that allowing for the appropriate number of evaluable participants and by checking self-report measures for completeness, we will have a full complement of data. Every effort will be made to encourage and facilitate participants' completion of all questionnaires and all items on the questionnaires for each study assessment. In the event that missing data occur, every effort will be made to contact participants via phone and obtain the data or to find out why the questionnaires or items are missing. The reasons for missing data will be documented. Missing questionnaire items will be treated in accordance with the documented scoring procedures. Although it is very unlikely that missing values will not occur randomly, we will confirm their randomness. Multiple imputation⁴⁵ will be applied to (1) give more accurate statistical tests and standard errors for key treatment effect parameters and to (2) give some indication of the sensitivity of the analyses to missing data. The causes and pattern of the missing data will be examined and taken into consideration in the design of future studies.

8.1.2. For audio-recordings, these will be uploaded to Box within a week of the interview/clinic visits and deleted from the digital audio recorder (Sony). The recordings will be transcribed by a professional transcription service, and the transcripts will be used for data analysis.

8.1.4. Data collected (both assessments and transcripts) will only be accessed by the following: 1) The research team and 2) The treating physician and their designee.

8.2. Data Analysis and Sample Size:

8.2.1. Analysis Plan for Aim 1

We anticipate thematic saturation will be reached with this number of participants based on past similar research (i.e., the point at which no new data emerge).^{19,20} All interviews will be conducted and audio-recorded by study personnel and then transcribed by a professional transcription service. Two trained personnel ("coders") will extract and highlight themes from the transcripts. We will analyze the qualitative data using grounded theory and constant comparative methods, with coding to structure data into categories and create groups according to the broader issues or themes.⁴⁶ The themes will focus on EOL care as it relates to older patients with AML and MDS, barriers and challenges to ACP and MOLST completion, potential solutions and ideas, experience

with telehealth interventions, added values of the intervention, support and concerns for the proposed intervention, components of the intervention that are important to them, and their opinions about the intervention (e.g., delivery, format). We will keep an audit trail to establish trustworthiness. We will critically examine the data collection and analysis process, discuss emerging codes, and reach consensus on principal themes. These themes will be used to adapt the telehealth-delivered ACP intervention.

8.2.2. Analysis Plan for Aim 2

Quantitative analyses: We anticipate that our proposed sample size will be sufficient based on prior research²² and also published guidance on usability study.^{47,48} We will employ descriptive statistics to summarize the data. Feasibility will be defined based on the retention rate (percentage of patients consented to the study ultimately completing all study components); >80% will be considered feasible. Recruitment rate (percentage of patients who are approached and agree to enroll) will also be described. Usability will be defined based on the Telehealth Usability Questionnaire completed by patients; total average of >5 will be considered usable.^{49,50} We anticipate that about 20% of the participants will withdraw before post-intervention assessment due to death.⁵¹ With 20 patients enrolled, we anticipate at least 16 patients to be evaluable. When we estimate retention rate and usability, a 95% CI will span approximately +/- 25%. For example, if we observe 12/16 (75%) patients complete the tasks, the CI will be 51-90%.

For other measures, these are being collected in preparation for a larger clinical trial in the future. As exploratory analyses, paired t-tests or McNemar's test will be used to evaluate change in measures from baseline to post-intervention.

Qualitative analyses will be per Aim 1. All audio-recorded interviews and clinic visits will audio-recorded by study personnel and then transcribed by a professional transcription service. The themes will focus on participant experience during the telehealth ACP visit and feedback which will be used to further optimize the study procedures and intervention.

For audio-recorded clinic encounters, we will assess EOL care concerns brought up by patients and caregivers. We will assess how the physician addresses these concerns. Quantitative analysis of the communication processes, including number of questions asked and topics discussed will be analyzed. We have previously used the same study procedures and coders will undergo extensive training and supervision by study investigators.

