2.3.1 Feasibility and usability metrics

The usability and feasibility of the adapted telehealth-delivered ACP intervention will be evaluated based on the following:

- a) Retention rate (percentage of patients who consented and completed the visit)
- b) Telehealth Usability Questionnaire (total average of >5 will be considered usable)

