3.3. Study Population

Aim 1: We will gather feedback from older patients with AML/MDS (N=5-10), caregivers (N=up to 2 caregivers per patient and therefore up to a total of 20 caregivers), oncology physicians (N=5-10), oncology APP and nurses (N=5-10), palliative care physicians (N=5-10), as well as palliative care APP and nurses (N=5-10). Therefore, the total number of participants will be between 25 and 70. We anticipate thematic saturation will be reached with this number of participants based on past similar research.^{19,20} For patients, we will consent up to 15 patients to account for screen fail or withdrawal.

Results from Aim 1 will be used to adapt the telehealth intervention for use in Aim 2. In other words, Aim 2 will occur after Aim 1 has been completed.

Aim 2: We will recruit 20 patients, their caregivers (up to 2 caregivers per patient), and oncology providers. We will consent up to 30 patients to account for screen fail or withdrawal.

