3.12. Vulnerable Subjects

Recruitment will exclude vulnerable populations such as fetuses, neonates, children, pregnant woman, prisoners, and institutionalized individuals. We will also exclude adults who are deemed to not have decisional capacity and those who lost their consent capacity during the study period, as per their treating oncologist.

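### The >80% retention rule, the expected 20% deaths and the 16-patient precision example do not fit together, and retention is defined in two ways

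*Combined protocol and SAP*

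**What the plan says.** Section 8.2.2 sets the feasibility criterion: "percentage of patients consented to the study ultimately completing all study components); >80% will be considered feasible". Section 7.2.2.17 uses the same numerator, "Retention rate (percentage of patients consented to the study ultimately completing all study components", and labels it the primary feasibility metric. Section 2.3.1 differs: "Retention rate (percentage of patients who consented and completed the visit", with no threshold.

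Section 8.2.2 then gives its planning figures: "We anticipate that about 20% of the participants will withdraw before post-intervention assessment due to death"; "With 20 patients enrolled, we anticipate at least 16 patients to be evaluable". It says that the 95% CI for retention and usability will span roughly plus or minus 25%, and illustrates: "For example, if we observe 12/16 (75%) patients complete the tasks, the CI will be 51-90"%.

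Two other sections bear on who is counted. Section 3.3 says "We will consent up to 30 patients to account for screen fail or withdrawal". Section 3.12 excludes "those who lost their consent capacity during the study period, as per their treating oncologist". Neither says what happens to these patients in the retention denominator.

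**The concern.** Within one paragraph of 8.2.2, the criterion is written over consented patients, the expected deaths use up the whole 20% allowance, and the precision example is computed on a group from which those deaths have already been removed. The reader cannot tell whether a patient who dies before the post-intervention assessment is a retention failure or is not counted.

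The numerator is also unsettled. A patient who attends the telehealth visit and dies before the post-intervention measures is retained under 2.3.1 and lost under 7.2.2.17 and 8.2.2. Section 7.1 allows up to 12 weeks after the visit for those measures, so this case can arise.

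Feasibility is half of the hypothesis in 2.3. With 20 patients, the choice of denominator can decide whether the intervention is called feasible, and at present that choice could be made after the data are known.

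**Working it through.** **Inputs from 8.2.2.** Enrolled n = 20; expected deaths d = 0.20; threshold strictly above 80%; precision example 12/16. Patients are treated as independent. Completion among patients who do not die first (s) is not given in the documents, so values other than 1 are assumptions.

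**Step 1: the plan's own figures.**
- Evaluable: 20 × (1 − 0.20) = 16.
- 12/16 = 75%, Wilson 95% CI 50.5% to 89.8%, which agrees with the stated interval.
- The plus or minus 25% fits the widest case at n = 16 (8/16, Wald ± 24.5 points).

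These figures reproduce; the difficulty is how they relate to the criterion.

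**Step 2: the written rule, 20 patients in the denominator.**
- 16/20 = 80.0% is not above 80%. The smallest passing count is 17/20 = 85%, so three losses of any cause are allowed against four expected deaths.
- P(pass) = P(X ≥ 17), X ~ Binomial(20, (1 − d) × s).

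| Deaths d | Completion s among the others | (1 − d) × s | P(pass) |
|---|---|---|---|
| 20% | 100% | 0.80 | 41% |
| 20% | 95% (assumed) | 0.76 | 26% |
| 20% | 90% (assumed) | 0.72 | 15% |
| 20% | 80% (assumed) | 0.64 | 4% |
| 15% (assumed) | 100% | 0.85 | 65% |
| 10% (assumed) | 100% | 0.90 | 87% |

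**Step 3: the denominator in the precision example.** With 16 patients, 13/16 = 81.25% is the smallest pass. P(X ≥ 13), X ~ Binomial(16, s), is 93% at s = 0.90 and 60% at s = 0.80. Expected deaths no longer count against the rule.

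**Step 4: the same completers on both denominators.** Twelve completers give 12/16 = 75% (51% to 90%) or 12/20 = 60% (Wilson 39% to 78%).

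**Step 5: other unsettled counts.**
- If 30 were consented and all counted, 25/30 would be needed against 30 × 0.80 = 24 expected; P(pass) at 0.80 is 43%.
- Capacity loss (illustration): with 16 completers, three deaths and one loss of consent capacity, keeping the last patient gives 16/20 = 80.0% (fails) and removing that patient gives 16/19 = 84.2% (passes).
- The wording that at least 16 will be evaluable treats an expected value as a floor: P(X ≥ 16), X ~ Binomial(20, 0.80), is 63%.

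**The case against.** The strongest reply is that deaths were never meant to count: the precision statement covers retention explicitly and uses 16, which is 20 less the expected deaths. That is a fair reading, and on it the conflict goes away. But the definition in both 7.2.2.17 and 8.2.2 says consented patients, and no sentence removes deaths, so the text needs correcting either way.

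A second reply is that a feasibility threshold need not be one the study expects to pass. That stands. Section 1.3 describes planning forms completed a median of 18 days before death in AML, so reaching patients in time may be part of feasibility, and counting deaths is a defensible strict choice. It should then be stated as a choice.

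Third, the stated interval width is not misleading. At n = 20 intervals are slightly narrower (15/20: 53% to 89%), so plus or minus 25% is conservative. The mismatch concerns who is counted. The 12/20 and 16/19 cases are illustrations, not results the plan predicts.

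A reader might infer that the feasibility verdict would largely measure mortality. The documents do not support that: deaths and non-completion enter as one product, and at 20% deaths the pass probability falls from 41% to 15% to 4% as completion among the others goes from 100% to 90% to 80%.

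A reader might also take the median survival of 6 to 12 months in 1.1 as confirming the 20%. It cannot. Assuming exponential survival from enrollment, deaths = 1 − 2^(−t/median), with 4.345 weeks per month. This runs from 10.5% (t = 1 month + 4 weeks = 1.92 months, median 12) to 42.3% (t = 2 months + 12 weeks = 4.76 months, median 6). Those medians refer to AML or high-risk MDS, while 3.4 admits any AML or MDS.

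**Conclusion.** The point holds as an internal mismatch. On the written definition with 20 patients, expected retention is at most 80.0% against 17/20 needed, with a 41% chance of passing at the plan's own death rate and no other loss. On the denominator used for precision, deaths drop out and the problem disappears. The visit-only definition in 2.3.1 adds a second inconsistency.

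It would go too far to say that the criterion cannot be met or that its level is wrong. A pass remains possible, and actual mortality may be below 20%. The 41% rests on exactly 20% deaths and independent patients; the 15% also rests on an assumed 10% loss among the others.

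Severity is modest: this is a descriptive secondary aim of a 20-patient pilot, and nothing in the documents ties the threshold to a go/no-go decision.

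**What to change.** Amend the text before Aim 2 outcomes are seen:

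1. Use the definition based on all components in 2.3.1, 7.2.2.17 and 8.2.2, and list the components and time window that count. Sections 4.1.4 (1–2 weeks) and 7.1 (4 weeks, up to 12) give different interview windows and must be reconciled.
2. State the denominator for the >80% rule.
   - If deaths are excluded, as the 16-patient example implies, exclude only patients who died while still on study and before any component's window had closed without completion. Keep withdrawals and patients who had already missed a component, even if they later died.
   - If deaths are kept, say that 17/20 is needed and that the expected value on the plan's own figures is 80.0%.
3. In either case report the all-consented and the death-excluded rate, each with a 95% CI, and the number of deaths before and after the visit.
4. Leave screen failures out of the denominator, and state how patients who lose consent capacity (3.12) are counted.
5. Base the precision statement on the chosen denominator (Wilson: 13/16, 57% to 93%; 16/20, 58% to 92%). Replace the promise of at least 16 evaluable with about 16 expected if death is the only loss.

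The cost is protocol wording only: no extra patients, visits or data. The downside of a death-excluded rate is that it does not show total attrition, which is why both rates should be reported.

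### The usability verdict uses a questionnaire scheduled only after the telehealth visit, so patients whose visit failed for technical or usability reasons may have no score and the result could be biased upward

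*Combined protocol and SAP*

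**What the plan says.** Section 8.2.2 sets two success rules for Aim 2. For usability: "Usability will be defined based on the Telehealth Usability Questionnaire completed by patients", and "total average of >5 will be considered usable". Section 2.3.1 gives the same cut-off. For feasibility, the retention rate decides: ">80% will be considered feasible".

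The TUQ has no baseline administration; its section is headed "7.2.3.9. Usability (Patient and caregiver) – post-intervention only". The Aim 2 table in 9.1.2 places it in a post-intervention window counted from the telehealth visit: four weeks, extendable to 12.

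On numbers, 8.2.2 says "We anticipate that about 20% of the participants will withdraw before post-intervention assessment due to death" and "With 20 patients enrolled, we anticipate at least 16 patients to be evaluable".

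The missing-data paragraph of 8.1.2 provides for telephone contact to recover questionnaires or learn why they are missing, documented reasons, a check that missingness is random, and multiple imputation, partly to show sensitivity to missing data.

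No section says how a patient whose visit failed, was abandoned or never took place enters the usability verdict.

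**The concern.** A patient who could not get the platform to work, or gave up partway, has had the worst usability experience in the study. Because the TUQ window runs from the visit, a patient whose visit never happened has no scheduled form, and a patient with an abandoned visit has no stated route to one. If such patients are missing from the average, it describes those who managed the visit and can look better than the experience of all who tried.

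The hypothesis in 2.3 is that the intervention will be feasible and usable, and the study prepares for a larger trial. In patients aged 60 and over, whether some cannot manage a video visit is part of what a usability pilot should find out.

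Two provisions might be expected to cover the gap, and neither does so fully. Retention counts a failed visit as a loss but does not distinguish it from a death. The imputation in 8.1.2 considers non-random missingness very unlikely, does not name the TUQ, and has no baseline TUQ to draw on. It would fill the scores of failed users largely from those of successful users. Observed data cannot confirm randomness when missingness depends on the unseen score.

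**Working it through.** **The plan's own figures.** Evaluable patients: 20 × (1 − 0.20) = 16, as stated. The worked interval for 12/16 reproduces with the Wilson formula (z = 1.96): (0.75 + 0.1201 ± 1.96 × √(0.75 × 0.25/16 + 3.8416/1024)) / 1.2401 = 50.5% to 89.8%, which rounds to the stated 51-90%. Neither figure is in dispute.

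**Retention.** 16/20 = 80% fails a rule of more than 80%; 17/20 = 85% passes with three patients lost. Section 3.3 allows up to 30 consents, so 20 completers of 24 consented (83%) would pass with four lost. Section 2.3.1 defines retention as completing the visit, while 7.2.2.17 and 8.2.2 require all study components. Under 2.3.1, a patient who had the visit but returned no TUQ still counts as retained.

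**Effect on the usability mean.** Let n completers have mean m, and let k living patients without a TUQ because of technical or usability failure be given score s. Deaths are left out.

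Sensitivity mean = (n × m + k × s) / (n + k)

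The documents do not give the TUQ item range; 1 to 7 is assumed here. The values of m, k and s are scenarios, not predictions. With n = 17:

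| m | k and s | Calculation | Mean | Above 5? |
|---|---|---|---|---|
| 5.3 | one scored 1 | (90.1 + 1)/18 | 5.06 | yes |
| 5.3 | two scored 1 | (90.1 + 2)/19 | 4.85 | no |
| 5.3 | two scored 3 | (90.1 + 6)/19 | 5.06 | yes |
| 5.3 | three scored 3 | (90.1 + 9)/20 | 4.96 | no |
| 5.5 | two scored 1 | (93.5 + 2)/19 | 5.03 | yes |
| 5.5 | three scored 1 | (93.5 + 3)/20 | 4.83 | no |
| 5.5 | three scored 3 | (93.5 + 9)/20 | 5.13 | yes |
| 6.0 | three scored 1 | (102 + 3)/20 | 5.25 | yes |

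**Break-even.** The completer mean at which the sensitivity mean equals exactly 5 is (5(n + k) − k × s)/n.

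- 18 completers, two failures: 98/18 = 5.44 (scored 1) to 92/18 = 5.11 (scored 4).
- 17 completers, three failures: 97/17 = 5.71 (scored 1); 91/17 = 5.35 (scored 3).
- 16 completers, all four losses technical: 96/16 = 6.00 (scored 1) to 84/16 = 5.25 (scored 4).

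A completer mean between 5 and the break-even value changes verdict; one above it does not. If the missing patients would have scored as the completers did, the shift is 0.

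**The case against.** A reader might infer that the plan restricts the average to completers, that the result is therefore biased upward, and that retention misses the problem. The documents do not support that reading.

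- **The wording.** Both patients and caregivers receive the TUQ, so the phrase about completion by patients may only say whose scores count. No analysis set is named.
- **The direction.** The only cause given for the expected loss is death. The TUQ is collected in person or by mail (7.2.3), not through the platform, so a patient who struggled can still return it. Section 7.1 supplies a tablet, internet access and instructions to patients without a device. Bias is possible, not established.
- **Retention.** A failed visit counts against retention under either definition. Passing at 17/20 with three technical failures requires no other loss. If each of the other 17 patients had an independent 20% chance of loss (illustrative, using the plan's figure), that has probability 0.8^17 = 2.3%. Meeting both rules while 3/20 = 15% could not use the intervention is possible but unlikely on the plan's own expectation.
- **Missing data.** Section 8.1.2 already requires follow-up and documented reasons, and interviews about the visit are planned.
- **The remedy.** Giving the lowest score to someone who rated nothing is a worst-case convention. Feasibility can reasonably carry failed visits while usability carries rated experience.

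These arguments make the concern conditional and show that the size depends on the scenario. They do not supply a rule for failed visits, and the imputation would not correct for them. The usability verdict is also reached separately from retention, so it can be favourable even when retention fails.

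**Conclusion.** The concern holds in conditional form. The handling of failed or abandoned visits in the usability verdict is unstated, and if such patients have no TUQ, the verdict could be biased upward. In the 17-completer scenarios, two or three technical failures can move a completer mean of 5.3 or 5.5 to 5 or below, or leave it above 5, depending on the score assigned; a mean of 6.0 survives three failures at the lowest score. This rests on an assumed 1-7 scale and on a number of technical failures that the documents do not give. If losses are deaths or otherwise unrelated to usability, nothing changes. This is a worthwhile, low-cost improvement to one of the two success rules and does not invalidate the pilot.

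**What to change.** In 8.2.2 and the Aim 2 table in 9.1.2:

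1. Offer the TUQ to every patient with an attempted visit, including failed or abandoned visits.
2. Keep the rule of more than 5 on observed scores.
3. Report the number of missing TUQs by reason (death, technical or usability failure, other) beside the mean.
4. Add one pre-specified sensitivity mean in which living patients without a TUQ who failed the visit for technical or usability reasons receive an unfavourable score: the lowest value, plus a milder value to show the range. Leave deaths out. State the TUQ item range so that these values are defined.
5. If only the observed mean exceeds 5, word the conclusion as *usable among those who completed the questionnaire*.

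The cost is one form for failed visits and one extra analysis; 8.1.2 already requires the reasons for missing data to be documented. The downside is that the usability figure may look less favourable.
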